2.1.3 Tertiary outcome measures

- a) Systolic and diastolic blood pressure will be measured as the mean of the second two readings at each sitting from day 2 to the last day of measurement
- b) Beat-to-beat variability in systolic blood pressure will be measured over 5 minutes as the coefficient of variation (standard deviation / mean) after automated and manual removal of artefacts and after removal of any linear trend in the data.
- c) Flow mediated slowing will be measured as the absolute reduction in speed of flow from the average value during baseline to the minimum valid reading during the first 30 seconds of recovery (assessed blind).
- d) Indices of resting state cerebral autoregulation (transfer function analysis derived gain, phase and coherence) will be determined by transfer function analysis according to the

protocol recommended in the CARNET White Paper, using the open access tfa script developed by [name] and made available via the CARNET collaboration.

- e) A voxel-wise general linear model based analysis of cerebrovascular reactivity on MRI will be performed with the FEAT.
- f) Estimates of CVR will be determined from the peak velocity achieved during each test (hyperventilation, 4% CO₂ and 6% CO₂) minus the baseline value, divided by the peak minus baseline etCO₂ values. Results will be expressed both as absolute and percentage change in mean velocity per mmHg change in etCO₂.

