Following the period of monitoring, reactivity to CO₂ will be assessed by 3 minutes of inhalation of 6% CO₂, delivered via a respiratory circuit with a non-invasive ventilation mask and harness, supplied with 2 alternating periods of medical air versus 6%CO₂/21%O₂/balance N₂. The resulting increase in MCA mean flow velocity on TCD will be related to the change in end-tidal CO₂ to determine the vasodilatory response, adjusted for any change in blood pressure. Secondly, the participant will be instructed to hyperventilate at 1 breath per second for 30 seconds to reduce etCO₂ and estimate change in mean flow velocity per unit change in etCO₂.

Peripheral Vascular Reactivity (10 minutes)

Effects of medication on peripheral endothelial function will be estimated by assessment of flow-mediated slowing (Vicorder, Skidmore Industries). This determines the change in speed of flow of the pressure waveform between two sites in the arm, before and after a short period of occlusion. This induces endothelium dependent vasodilatation, which results in slowing of the speed of blood flow. If the previous tests last >60 minutes to achieve accurate measurements, or if the participant finds this procedure too uncomfortable this element may be omitted at follow up visits.

Blood pressure monitoring

Patients will be provided with a home blood pressure monitor to record their blood pressure twice daily (on waking and evening), recorded three times at each sitting, for 7 days prior to their subsequent study visit (A&D UA-767 BT). Patients will be asked to record their blood pressure readings and return them for

assessment of how allocated treatment affects blood pressure, and how this may interact with the primary outcome measure. If potential symptoms of hypotension occur, patients may be requested to perform additional readings for clinical safety purposes. Participants will be asked to record any side-effects on the same diary card as used for blood pressure monitoring.

Medication Dispensation

Study medication / placebo will be dispensed by the Oxford University Clinical Trials Pharmacy after randomisation.

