 - g) Alternative estimates of CVR (change in mean flow velocity per unit change in etCO₂) determined during hyperventilation, 4% CO₂ and 6% CO₂, each versus air.

2. Trial design

OxHARP is a randomised, placebo and actively controlled, three-arm double-blind (patient and clinician), assessor-blinded crossover trial. Using random allocation, participants will have three weeks of treatment with each of the following: sildenafil (25mg TDS, titrated to 50mg TDS after one week), placebo (one tablet TDS, titrated to 2 tablets after one week), cilostazol (50mg BD, titrated to 100mg BD after one week, with midday placebo). Following each treatment period, participants will undergo a clinical and physiological assessment, followed by at least one week washout before starting the next treatment. A subgroup of participants will undergo MRI imaging following sildenafil and placebo treatments to assess arterial pulsatility on MRI and cerebrovascular reactivity, and a further subgroup will undergo MRI on all three treatments. The primary objective will be assessed using a superiority hypothesis testing framework and a non-inferiority framework will be used for the secondary objective.

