2.1.2 Secondary outcome measures

Percentage change in middle cerebral artery mean flow velocity per mmHg increase in concurrent end-tidal CO₂ on TCD ultrasound will be estimated by the unstandardized beta-coefficient from an unadjusted linear regression between the end-tidal CO₂ and MCA mean velocity during inhalation of 90 seconds of air, 2 minutes 4% CO₂, 2 minutes of air and 2 minutes of 6% CO₂, assessed following three weeks of treatment ('CVR'). Prior to linear regression procedure, any time delay between the etCO₂ waveform and the MCA MV will be estimated by the maximum R value in a standard cross-correlation analysis, and the etCO₂ trace shifted by this value. The side of insonation will be selected by the same quality assurance method as for MCA-PI. A sensitivity analysis will be performed using the standardised beta-coefficients for increase in blood flow velocity per increase in end-tidal CO₂.

Cerebrovascular reactivity on MRI during inhalation of air or 6% CO₂ in 2 minutes intervals (boxcar design) will be estimated as the percentage change in BOLD signal per mmHg change in end-tidal CO₂, estimated from the beta-coefficient of a general linear model between each voxel time-series and a phase-shifted etCO₂ trace shifted by the time-delay with the maximum r^2 by cross-correlation (FSL FEAT). The core ROIs will be normal-appearing white matter voxels and white matter voxels within a white matter hyperintensity on a 'BIANCA' mask. Secondary ROIs include total white matter, white matter hyperintensities and superficial and deep grey matter masks. BOLD scans will be preprocessed with the fMRI Expert Analysis Tool from the fMRI software library (FEAT), including field-map based bias field correction, high pass temporal filtering (300s cycle length), motion correction (MCFLIRT) and registration to structural (FLIRT) and standard space (FNIRT).

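### The tertiary hyperventilation reactivity estimate in SAP 2.1.3(f) is defined by peak values, although the test lowers end-tidal CO₂; read as maxima, it is an unstable ratio of two small differences

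*SAP*

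**What the plan says.** Tertiary objective 3(g), listed in SAP 1.3 among the exploratory and mechanistic aims, covers "Alternative estimates of CVR (change in mean flow velocity per unit change in etCO₂) determined during hyperventilation, 4% CO₂ and 6% CO₂, each versus air".

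SAP 2.1.3(f) gives the rule for all three tests. The numerator is set by "Estimates of CVR will be determined from the peak velocity achieved during each test (hyperventilation", with 4% and 6% CO₂ named next in the same bracket, less the baseline value, and this is "divided by the peak minus baseline etCO₂ values". On the scale it adds: "Results will be expressed both as absolute and percentage change in mean velocity per mmHg change in etCO₂".

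Protocol 8.5 (CO₂ reactivity) describes the test itself. The participant is told to "hyperventilate at 1 breath per second for 30 seconds to reduce etCO₂ and estimate change in mean flow velocity per unit change in etCO₂".

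Neither document defines a lowest value, trough or largest deviation for hyperventilation.

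**The concern.** For 4% and 6% CO₂, etCO₂ and velocity are expected to rise, so a maximum captures the response. Hyperventilation is meant to push etCO₂ down. Velocity should follow it down; the documents do not say so, but it follows from the positive velocity-to-CO₂ relation that the trial sets out to measure. In a falling trace the maximum lies near the start, before the response has developed. An analyst who codes item (f) as written would then divide one small difference by another, each about the size of the measurement noise.

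At stake is whether the hyperventilation estimate measures reactivity at all, and whether two analysts following the same sentence would get the same answer.

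**Working it through.** **Inputs from the documents.** The formula (SAP 2.1.3(f)), and the direction and 30-second length of the test (Protocol 8.5). The plan states no expected value, variance or sample size for this outcome, so there is no figure of its own to reproduce.

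**Assumed inputs.** Baseline mean velocity 50 cm/s; baseline etCO₂ 38 mmHg; true slope 1.5 cm/s per mmHg (3% of 50); exponential fall with a 10-second time constant towards a total fall d of 5, 10 or 15 mmHg; one reading per second for 30 seconds; baseline averaged over 30 readings; per-reading noise SD (velocity / etCO₂) of 1/0.5, 2/1 or 3/1.5; 20,000 simulated tests per setting.

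**Step 1: the sign.** CVR = (V_test − V_base) / (etCO₂_test − etCO₂_base). If both quantities fall and the fallen values are used, for example from 50 to 35 cm/s and from 38 to 28 mmHg, then CVR = (35 − 50)/(28 − 38) = (−15)/(−10) = +1.5. Two falls give a positive ratio, which is the right sign.

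**Step 2: the size of the differences.** Without noise, the etCO₂ deviation at second t is −d(1 − exp(−t/10)). With d = 10:

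- t = 1 (the highest point): −10 × (1 − 0.905) = −0.95 mmHg, and velocity 1.5 × (−0.95) = −1.43 cm/s.
- t = 30 (the lowest point): −10 × (1 − 0.050) = −9.50 mmHg, and velocity 1.5 × (−9.50) = −14.25 cm/s.

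Both ratios equal 1.5 without noise. At the highest point, however, the denominator is under 1 mmHg, about the size of the assumed etCO₂ noise (SD 0.5 to 1.5). Taking a maximum also selects upward noise, so either difference can cross zero.

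**Step 3: simulation (true value 1.5).**

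| Total fall (mmHg) | Noise SD (cm/s / mmHg) | Maxima for both: median [5–95%] | Negative | Lowest for both: median [5–95%] | Negative |
|---|---|---|---|---|---|
| 5 | 1 / 0.5 | 0.47 [−7.63, 9.14] | 39.9% | 1.57 [1.36, 1.82] | 0% |
| 5 | 2 / 1 | 0.13 [−13.52, 13.72] | 47.9% | 1.64 [1.30, 2.08] | 0% |
| 5 | 3 / 1.5 | 1.29 [−15.24, 17.68] | 28.2% | 1.69 [1.26, 2.27] | 0% |
| 10 | 1 / 0.5 | 1.35 [−0.71, 6.31] | 10.8% | 1.54 [1.41, 1.67] | 0% |
| 10 | 2 / 1 | 0.48 [−7.97, 8.92] | 40.3% | 1.57 [1.36, 1.83] | 0% |
| 10 | 3 / 1.5 | −0.08 [−11.57, 10.09] | 51.3% | 1.61 [1.32, 1.96] | 0% |
| 15 | 1 / 0.5 | 1.47 [0.29, 3.97] | 2.1% | 1.52 [1.43, 1.62] | 0% |
| 15 | 2 / 1 | 1.07 [−4.42, 7.86] | 22.3% | 1.55 [1.39, 1.73] | 0% |
| 15 | 3 / 1.5 | 0.43 [−8.69, 9.39] | 41.2% | 1.58 [1.36, 1.83] | 0% |

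A mixed reading, highest velocity with lowest etCO₂, gave medians from −0.30 to 0.14, with 2% to 90% of values negative.

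**Step 4: what the table shows.** With maxima, the result is acceptable only where the fall is large and the noise small. Lowest values for both gave a usable estimate in all nine settings. They overshoot slightly, by at most (1.69 − 1.5)/1.5 = 13%, because single extremes pick up noise.

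**The case against.** The strongest reply is that *peak* means peak response, that is, the largest deviation in whichever direction the test drives. Item (f) and objective 3(g) both speak of change rather than increase, and Protocol 8.5 states the purpose of hyperventilation plainly. On that reading the formula works. This is a plausible account of intent, and it stands as such. But the SAP does not say it. In the same list, item (c) on flow mediated slowing asks for a minimum where a minimum is wanted, while item (f) names hyperventilation and still asks for the peak.

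A second reply is that SAP 5.3 has derived indices calculated by assessors blind to treatment, so settling the word later need not favour a drug. That is fair as to bias. It does not settle which value is computed. The before-data-lock requirement in SAP 5.3 also covers only the primary and secondary analyses, and SAP 2.5 lets tertiary analyses run for two years after the last visit.

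A third reply is that the instability rests on invented noise levels and an invented fall. That is correct about its size, and the table shows how widely the size varies.

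**Conclusion.** The wording of 2.1.3(f) does not fit hyperventilation. Read as maxima, it gives a noise-dominated ratio in most of the settings tried: medians from −0.08 to 1.47 against a true 1.5, 2% to 51% of values negative, and a widest 5–95% range of about −15 to 18. These figures rest on the assumed baseline, slope, shape and size of fall, sampling rate and noise, and on velocity falling with etCO₂.

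A reader might infer three stronger things that are not supported:

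- **That the formula reverses the sign.** It does not: two falls give a positive ratio, and with two maxima the sign is unreliable rather than systematically wrong.
- **That the ratio is undefined.** It is unstable, because its denominator is small and noisy.
- **That the outcome is meaningless in every participant.** With a 15 mmHg fall and the lowest noise, the literal rule gave a median of 1.47 with 2.1% of values negative.

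The reach is narrow: one of three tests within one tertiary measure. The 4% and 6% CO₂ estimates keep a suitable definition. The secondary CVR outcome is a regression over "90 seconds of air, 2 minutes 4% CO₂, 2 minutes of air and 2 minutes of 6% CO₂" and uses no hyperventilation data. The primary outcome, MCA-PI, is untouched. This is a minor point, worth correcting because correction is so cheap.

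**What to change.** Add one sentence to SAP 2.1.3(f): for hyperventilation, the lowest mean velocity and the lowest etCO₂ during the test replace the peak values, each minus baseline; the peak definition stays for 4% and 6% CO₂. Ideally this is done before the tertiary indices are derived.

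As an optional refinement, take each extreme as a short average over a stated number of beats or seconds, which should reduce the slight overshoot of single lowest values. The same could apply to the peaks in the CO₂ tests.

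The cost is one sentence in the SAP. It needs no new data, no change to the visits or test procedure, and no change to any primary or secondary analysis.

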2.2 Randomisation and blinding

The random allocation of each participant to one of six of treatment sequences (arms) is by simple randomisation. The schedule will be created and details maintained by the Huddersfield PMU and participants will be assigned at their baseline visit. The participants, the study team and the trial statistician are blinded to treatment allocation. In participants in the MRI substudy with imaging performed only on placebo and sildenafil, the study team are unblinded to the cilostazol treatment arm, but the participants remain blinded.

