8.4. Randomisation, blinding and code-breaking

Randomisation will be performed by the Huddersfield PMU at the point of overencapsulation of medication in advance of provision of treatments to the Oxford Clinical Trial pharmacy. Study numbers will then be provided in sequence to participants at the Oxford Clinical Trial pharmacy. Each sequential study ID will be randomly allocated to one of six different treatment schedules, as outlined in the drug allocation

table on page 11, to produce three groups of 12 and three groups of 13 patients. The randomisation schedule will be generated by Huddersfield PMU.

The study will be blinded to the participant, blinded to the core study team ([name], [name], [name]) and blinded to the endpoint assessors (TCD measurement and MRI analysis). In patients consenting to the MRI substudy, the Trials pharmacy (or [name], who is otherwise independent of the study), will identify the visit at which the participant will be taking cilostazol so that the MRI scans can be arranged, but will not inform the patient or core team when sildenafil or placebo are assigned.

If clinical need requires unblinding of a specific patient, this will be done by the study pharmacist who will retain the randomisation schedule, following formal discussion with the Chief Investigator. Due to the low risk level associated with the study medication, and no specific medical intervention indicated for any potential complication that requires prior knowledge of current study treatment, emergency out of hours code-breaking is not required.

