11. STATISTICS

11.1. Description of Statistical Methods

A statistical analysis plan will be signed off prior to analysis.

Primary outcome :

Change in Gosling's Pulsatility Index from baseline to follow up, utilising the visually-assessed, better quality TCD recording (defined by blinded assessor) will be compared between sildenafil and placebo phases by paired T-test, comparing change in MCA-PI from baseline to after 3 weeks of treatment.

Secondary outcome:

The non-inferiority analysis will be based on the 95% CI for the mean change difference between sildenafil and cilostazol. If the upper 97.5% confidence limit is less than 0.08 units (2/3 of the clinically estimated overall cilostazol effect), non-inferiority will be declared.

Differences in reactivity to CO₂ from baseline in each of three states (sildenafil, cilostazol, placebo) will be compared by mixed-effect general linear models, with post-hoc pairwise comparison.

Tertiary outcomes

Equivalent statistical techniques will be used to determine responses to each of the further physiological measures for sildenafil versus placebo as the primary comparison (paired t-test for continuous outcomes), and mixed-effect linear models across the three groups. MRI imaging outcomes will be compared by analysis tools within the FSL software library, utilising linear models for interaction between drug allocation and BOLD-response to carbon dioxide. Secondly, the relevance of derived physiological indices including home blood pressure, arterial stiffness, cerebral autoregulation, peripheral vascular reactivity and beat-to-beat blood pressure variability will be determined both as predictors of cerebral pulsatility and autoregulation in linear models, and for the interaction between drug class and these indices on cerebral pulsatility and reactivity.

Individuals missing either sildenafil or placebo interventions will be excluded from the analysis corresponding to the primary objective but included in the safety analysis. Participants without cilostazol exposure will be included in the sildenafil-placebo comparison, but not in the - secondary and tertiary analyses.

Safety data will be presented for all patients who are randomised and receive at least one dose of one treatment. Safety data will be summarised descriptively.

Genetic / biochemical predictors of response to treatment will be assessed by mixed linear models for continuous outcomes, and paired t-test for binary measures.

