5.1 Primary outcome

Gosling's MCA-PI will be compared between sildenafil and placebo treatment by paired t-test and a 95% confidence interval if normality distribution assumptions hold, or the non-parametric Wilcoxon signed rank test. If the placebo phase is not available, a comparison between the baseline value and sildenafil period will be accepted. The analysis will be re-run using the PP population as a sensitivity analysis, and using the percentage change at each phase from baseline.

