5.2 Secondary outcomes

The percentage change in mean blood flow velocity per mmHg during inhalation of air, 4% and 6% carbon dioxide versus medical air estimated from the beta-coefficient from a phase-shifted linear regression will be compared between sildenafil and placebo treatment by paired t-test and a 95% confidence interval if normality distribution assumptions hold, or the non-parametric Wilcoxon signed rank test. The analysis will be re-run using the PP population as a sensitivity analysis, and using the percentage change from baseline.

A non-inferiority analysis will be based on the 95% CI for the mean change difference between sildenafil and cilostazol. If the upper 97.5% confidence limit is less than 0.08 units (=inferiority margin, 2/3 of the clinically estimated overall cilostazol effect), non-inferiority will be declared. The data will be transformed if normality assumptions do not hold. The PP population will be used for this analysis, with the ITT population being used in a sensitivity analysis.

Differences in reactivity to CO₂ from baseline in each of three states (sildenafil, cilostazol, placebo) will be compared by mixed-effect general linear models, with post-hoc pairwise comparison, using the ITT population with the PP population being used in a sensitivity analysis. This will apply to both TCD measures of CO₂ reactivity and by ROI on MRI. On MRI, these analyses will also be performed on a voxel-wise basis by use of the FLAME tool (FSL).

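### SAP 5.1 lets baseline stand in for a missing placebo phase in the primary analysis, although protocol 11.1 excludes those participants; an unnamed period term and conflicting allocation wording are lesser points

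*SAP*

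**What the plan says.** **Missing placebo phase.** Protocol 11.1: "Individuals missing either sildenafil or placebo interventions will be excluded from the analysis corresponding to the primary objective". SAP 5.1, for the same analysis: "If the placebo phase is not available, a comparison between the baseline value and sildenafil period will be accepted". SAP 5.3 rules out any adjustment for missing data other than imputing a missing baseline. Protocol 11.5 leaves the handling of missing data to the SAP.

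**Period.** Protocol 11.1 says the primary outcome "will be compared between sildenafil and placebo phases by paired T-test", and SAP 5.1 that it "will be compared between sildenafil and placebo treatment by paired t-test and a 95% confidence interval", with a signed-rank test as fallback. For sildenafil against cilostazol, SAP 5.2 says: "A non-inferiority analysis will be based on the 95% CI for the mean change difference between sildenafil and cilostazol". CO2 reactivity in the three states "will be compared by mixed-effect general linear models, with post-hoc pairwise comparison, using the ITT population". None of these names period, which appears only in descriptive tables (adherence in SAP 3.2, adverse events in SAP Table 6.2).

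**Allocation.** Protocol 8.4 allocates study IDs to the six schedules "to produce three groups of 12 and three groups of 13 patients". SAP 2.2 says: "The random allocation of each participant to one of six of treatment sequences (arms) is by simple randomisation".

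**The concern.** The two documents give opposite instructions for the same participants in the primary test: anyone with a sildenafil measurement but no placebo measurement is left out under one and kept under the other.

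The choice has consequences. The outcome is change from baseline, and in a complete pair baseline cancels, leaving sildenafil minus placebo. Putting baseline in place of placebo amounts to assuming a placebo change of exactly zero. Baseline is measured before any treatment and before the randomised order begins. Familiarisation, regression to the mean, a placebo response or a change over calendar time would therefore enter as if it were drug effect, always in the same direction. More participants would not remove it.

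Period is a different matter. In a three-period crossover, a change common to all participants between periods goes into the error variance of an unadjusted paired difference. The non-inferiority comparison sets the sample size and has no power to spare at the planning SD.

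**Working it through.** **1. The plan's own sizes** (protocol 11.3, SAP 2.3).
- Primary: effect 0.12, SD of differences 0.2, two-sided 5%, 90% power. Normal approximation: (0.2 × 3.242 / 0.12)² = 29.2. The exact paired t calculation gives 32 (power 0.908), and 32/0.85 = 37.6, so 38.
- Non-inferiority: within-subject variance 0.02, so SD of differences √(2 × 0.02) = 0.2; margin 0.08, one-sided 2.5%. (0.2 × 3.242 / 0.08)² = 65.7, so 66, and 66/0.88 = 75. Exact t power at 66 is 0.893.

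Both reproduce. The planned standard error at 66 is 0.2/√66 = 0.025.

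**2. Baseline substitution.** Assume a common linear drift of b PI units per period, also running from baseline to the first on-treatment visit. A participant who takes sildenafil in period k contributes a drift of kb to sildenafil minus baseline.
- Placebo lost by drop-out after sildenafil: sildenafil precedes placebo in sequences 1, 2 and 3, in periods 1, 1 and 2. Mean shift (4/3)b = 1.33b.
- Placebo lost for reasons unrelated to sequence: sildenafil's mean period is 2, so the mean shift is 2b.

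Bias = mean shift × proportion of pairs substituted. At b = 0.05:

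| Pairs substituted | Shift 1.33b | Shift 2b |
|---|---|---|
| 5% | 0.003 | 0.005 |
| 12% | 0.008 | 0.012 |

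That is about 3–10% of the 0.12 target and roughly 0.1–0.5 of the standard error. The 12% equals the whole drop-out allowed for in the total of 75. The sample-size text allows 15% for the primary comparison; 2 × 0.05 × 0.15 = 0.015, about 0.6 of the standard error.

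**3. Period, complete pairs.** Over sequences 1 to 6 the period-number difference is −1, −2, −1, 1, 1, 2 for sildenafil minus placebo, and −2, −1, 1, 2, −1, 1 for sildenafil minus cilostazol. Each has mean 0 and mean square 2. Drift therefore adds no bias on average, and the unadjusted variance of a difference is 0.04 + 2b². The confidence interval widens by √(1 + 2b²/0.04): 2%, 6% and 22% at b = 0.03, 0.05 and 0.10.

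Non-inferiority power at n = 66, unadjusted:

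| Assumed b | Equal groups | Simple randomisation |
|---|---|---|
| 0 | 0.893 | 0.893 |
| 0.03 | 0.884 | 0.879 |
| 0.05 | 0.868 | 0.855 |
| 0.10 | 0.785 | 0.743 |

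One-sided type I error stays near 2.5% under simple randomisation and falls to 1.9% and 0.8% at b = 0.05 and 0.10 with equal groups. Primary power at 66 is at least 0.975 throughout. With period adjustment, simulated non-inferiority power is 0.890–0.895 (equal groups) or 0.882–0.886 (simple), with error of 2.4–2.6%.

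**4. Break-even for adjustment.** With no drift under simple randomisation, the mean interval width is 0.0996 adjusted and 0.0980 unadjusted, a variance ratio of (0.0996/0.0980)² = 1.033. Setting 2b²/0.04 = 0.033 gives b of about 0.025.

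**5. Allocation.** Simple randomisation of 75 to six sequences gives three groups of 12 and three of 13, in any order, with probability 20 × 75!/(12!³ 13!³ 6⁷⁵) = 0.0008.

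**The case against.** Protocol 11.5 delegates missing-data procedure to the SAP, so SAP 5.1 could be read as using that authority. But general delegation does not cancel an express exclusion in 11.1, and SAP 5.3 makes no exception for a missing placebo phase.

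SAP 5.1 also re-runs the primary analysis in the per-protocol population, which requires completed treatments (SAP 3.3) and so appears to drop substituted participants. It drops others as well, for example for major deviations, so it does not isolate the effect of substitution and does not settle the primary result.

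The SAP's document history cites protocol 3.0, whereas the protocol's amendment table lists only version 2.0, so a later text might have resolved a conflict. That should be checked. The SAP states that it rests on the latest protocol, yet it explains neither difference.

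On period, the objection largely stands. The paired test is valid without adjustment, no document gives a period effect, and a material loss needs b of about 0.05, a shift of 0.10 from period 1 to period 3. The planning SD is described as conservative: if it were 0.18 (assumed), power at b = 0.05 under simple randomisation would still be 0.91. The mixed model lists no covariates, so period there is unspecified rather than excluded.

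**Conclusion.** The conflict over a missing placebo phase is real and affects the primary analysis. The likely bias is small: 0.003–0.012 PI units, given a linear drift of 0.05 per period starting at baseline and 5–12% of pairs substituted. Both inputs are assumptions, and the upper end needs a share equal to all planned drop-out to have sildenafil but no placebo. A reader might infer that substitution could by itself produce a positive primary result. These sizes do not support that; the objection is to an avoidable, one-directional error in a randomised, blinded comparison.

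Naming period is a cheap secondary improvement. A reader might infer that its absence biases the treatment comparisons or inflates false positives. With complete pairs it does neither: error is nominal or conservative under both allocation schemes, and the cost is precision, mainly for non-inferiority.

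The allocation conflict is a matter of wording. A reader might infer that it undermines the randomisation or the analysis. The documents do not show that: the two descriptions cannot both be literal, but the analysis uses the sequences actually given.

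**What to change.** 1. **Primary analysis set.** Amend SAP 5.1 to apply the protocol 11.1 exclusion in the primary analysis, and report baseline substitution only as a labelled sensitivity analysis, separate from the per-protocol re-run. This needs no new data and costs only the substituted pairs; primary power has ample reserve.
2. **Period.** Before unblinding, pre-specify a period-adjusted estimate for the sildenafil–placebo and sildenafil–cilostazol contrasts. One form regresses each paired difference on signed indicators for periods 2 and 3 (+1 if sildenafil was given in that period, −1 if the comparator was), with the intercept as the contrast. The alternative is a model with treatment, period and participant, which adds a common-variance assumption. Name period in the CO2-reactivity mixed model. Report the unadjusted paired t-test alongside. If the adjusted estimate becomes primary, amend protocol 11.1 or declare a deviation. The cost is two degrees of freedom. With no drift it loses about 1 point of non-inferiority power under simple randomisation (0.884 against 0.893) and a negligible amount under near-equal groups. A period term does not model individually prolonged washouts, so the gain may be smaller than shown.
3. **Allocation.** State in protocol 8.4 and SAP 2.2 the scheme actually used to generate the schedule.
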